**Table 15: Baseline Coagulation**

Data set: All Randomized Patients			
	Number of Patients (%)		
	RT+BSC N = **	BSC N = **	Total N=**
INR			
Grade 0	** (**)	** (**)	** (**)
Grade 1	** (**)	** (**)	** (**)
Grade 2	** (**)	** (**)	** (**)
Grade 3	** (**)	** (**)	** (**)
Grade 4	** (**)	** (**)	** (**)
Not reported 	** (**)	** (**)	** (**)

 Not done or outside the 14-day window prior to start of randomization

**Table 16: Concomitant Medications at Baseline**

Data set: All Randomized Patients			
	Number of patients (%)		
	RT+BSC N = **	BSC N = **	Total N=**
Any concomitant medication 			
No	** (**)	** (**)	** (**)
Yes	** (**)	** (**)	** (**)

 Any medication taken within 14 days prior to randomization.

**Table 17: Summary of Radiotherapy**

Data Set: All Radiotherapy Treated Patients		
	Within 30 days for patients on RT+BSC (%)	After 30 days for patients on BSC (%)
Number of Fractions		
N	**	**
Median	**	**
Min - Max	** - **	** - **
Maximum Planned Dose		
N	**	**
Median	**	**
Min - Max	** - **	** - **
Type of Motion Management		
None	** (**)	** (**)
ABC	** (**)	** (**)
4D CT	** (**)	** (**)
Other	** (**)	** (**)
Beam Arrangement		
APPA	** (**)	** (**)
Oblique POP	** (**)	** (**)
Other	** (**)	** (**)
Planning		
3D conformal	** (**)	** (**)
IMRT	** (**)	** (**)
VMAT	** (**)	** (**)
Other	** (**)	** (**)
Position Verification		
None	** (**)	** (**)
kV 2D	** (**)	** (**)
MV 2D	** (**)	** (**)
CBCT	** (**)	** (**)
Other	** (**)	** (**)

**Table 18: Volumes of Radiotherapy**

Data Set: All Radiotherapy Treated Patients		
	Within 30 days for patients on RT+BSC (%)	After 30 days for patients on BSC (%)
Liver Volume (cc)		
N	**	**
Median	**	**
Min - Max	** - **	** - **
GTV Contoured		
Yes	** (**)	** (**)
No	** (**)	** (**)
GTV Value (cc)		
N	**	**
Median	**	**
Min - Max	** - **	** - **
CTV Value (cc)		
N	**	**
Median	**	**
Min - Max	** - **	** - **
PTV Value (cc)		
N	**	**
Median	**	**
Min - Max	** - **	** - **

**Table 19: Doses of Radiotherapy**

Data Set: All Radiotherapy Treated Patients		Within 30 days for patients on RT+BSC N (%)	After 30 days for patients on BSC N (%)
Percent of ModPTV Encompassed by 8 Gy Prescribed Dose (%)			
N		**	**
Median		**	**
Min - Max		** ** —	** ** —
ModPTV Dose (Gy)			
N		**	**
Median		**	**
Min - Max		** ** —	** ** —
Maximum Dose to PTV (Gy)			
N		**	**
Median		**	**
Min - Max		** ** —	** ** —
Spinal Canal Maximum Dose (Gy)			
N		**	**
Median		**	**
Min - Max		** ** —	** ** —
Liver Mean Dose (Gy)			
N		**	**
Median		**	**
Min - Max		** ** —	** ** —
Right Kidney Mean Dose (Gy)			
N		**	**
Median		**	**
Min - Max		** ** —	** ** —
Left Kidney Mean Dose (Gy)			
N		**	**
Median		**	**
Min - Max		** ** —	** ** —
Bilateral Kidneys Mean Dose (Gy)			
N		**	**
Median		**	**
Min - Max		** ** —	** ** —
Stomach Dose Contoured			
Yes		** (**)	** (**)
No		** (**)	** (**)
Stomach Maximum Dose (Gy)			
N		**	**
Median		**	**
Min - Max		** ** —	** ** —
Duodenum Dose Contoured			
Yes		** (**)	** (**)
No		** (**)	** (**)
Duodenum Maximum Dose (Gy)			
N		**	**
Median		**	**
Min - Max		** ** —	** ** —

**Table 19 (Continued): Doses of Radiotherapy**

Data Set: All Radiotherapy Treated Patients		Within 30 days for patients on RT+BSC N (%)	After 30 days for patients on BSC N (%)
Small Bowel Dose Contoured			
Yes		** (**)	** (**)
No		** (**)	** (**)
Small Bowel Maximum Dose (Gy)			
N		**	**
Median		**	**
Min – Max		** ** —	** ** —
Large Bowel Dose Contoured			
Yes		** (**)	** (**)
No		** (**)	** (**)
Large Bowel Maximum Dose (Gy)			
N		**	**
Median		**	**
Min - Max		** ** —	** ** —
Peritoneal Dose Contoured			
Yes		** (**)	** (**)
No		** (**)	** (**)
Peritoneal Maximum Dose (Gy)			
N		**	**
Median		**	**
Min - Max		** ** —	** ** —

**Table 20: Pain/Discomfort and Medication Assessment at Day 30 and Day 90**

Data Set: All Randomized Patients		
	RT + BSC (%)	BSC (%)
Completion of Assessment at baseline		
Yes	** (**)	** (**)
No	** (**)	** (**)
Reason of Not Complete at baseline		
Patient too ill	** (**)	** (**)
Not documented / recalled	** (**)	** (**)
Patient confused	** (**)	** (**)
Patient refused for reason other than illness	** (**)	** (**)
Other	** (**)	** (**)
Completion of Assessment at Day 30		
Yes	** (**)	** (**)
No	** (**)	** (**)
Reason of Not Complete at Day 30		
Patient too ill	** (**)	** (**)
Not documented / recalled	** (**)	** (**)
Patient confused	** (**)	** (**)
Patient refused for reason other than illness	** (**)	** (**)
Other	** (**)	** (**)
Completion of Assessment at Day 90		
Yes	** (**)	** (**)
No	** (**)	** (**)
Reason of Not Complete at Day 90		
Patient too ill	** (**)	** (**)
Not documented / recalled	** (**)	** (**)
Patient confused	** (**)	** (**)
Patient refused for reason other than illness	** (**)	** (**)
Other	** (**)	** (**)

**Table 21: Summary of BPI Scores at Baseline, Day 30 and Day 90**

Data set: All Randomized Patients						
	Baseline		Day 30		Day 90	
	RT+BSC	BSC	RT+BSC	BSC	RT+BSC	BSC
Worst pain						
N	**	**	**	**	**	**
Mean (standard deviation)	** (**)	** (**)	** (**)	** (**)	** (**)	** (**)
Pain at its least						
N	**	**	**	**	**	**
Mean (standard deviation)	** (**)	** (**)	** (**)	** (**)	** (**)	** (**)
Average pain						
N	**	**	**	**	**	**
Mean (standard deviation)	** (**)	** (**)	** (**)	** (**)	** (**)	** (**)
Pain Now						
N	**	**	**	**	**	**
Mean (standard deviation)	** (**)	** (**)	** (**)	** (**)	** (**)	** (**)
Percentage relief in pain by treatment						
N	**	**	**	**	**	**
Mean (standard deviation)	** (**)	** (**)	** (**)	** (**)	** (**)	** (**)
Pain interference with general activity						
N	**	**	**	**	**	**
Mean (standard deviation)	** (**)	** (**)	** (**)	** (**)	** (**)	** (**)
Pain interference with mood						
N	**	**	**	**	**	**
Mean (standard deviation)	** (**)	** (**)	** (**)	** (**)	** (**)	** (**)
Pain interference with walking ability						
N	**	**	**	**	**	**
Mean (standard deviation)	** (**)	** (**)	** (**)	** (**)	** (**)	** (**)
Pain interference with normal work						
N	**	**	**	**	**	**
Mean (standard deviation)	** (**)	** (**)	** (**)	** (**)	** (**)	** (**)
Pain interference with relationship						
N	**	**	**	**	**	**
Mean (standard deviation)	** (**)	** (**)	** (**)	** (**)	** (**)	** (**)
Pain interference with sleep						
N	**	**	**	**	**	**
Mean (standard deviation)	** (**)	** (**)	** (**)	** (**)	** (**)	** (**)
Pain interference with enjoyment of life						
N	**	**	**	**	**	**
Mean (standard deviation)	** (**)	** (**)	** (**)	** (**)	** (**)	** (**)

**Table 22: Proportion of Patients Experiencing a Significant Improvement in Symptoms**

	RT+BSC N (%)	BSC N (%)	P-value
All patients who had baseline and day 30 assessments Experiencing a Significant Improvement in Symptoms  at Day 30 from baseline	** (**.**)	** (**.**)	0.*** 
HCC patients who had baseline and day 30 assessments Experiencing a Significant Improvement in Symptoms  at Day 30 from baseline	** (**.**)	** (**.**)	0.***
Liver metastases patients who had baseline and day 30 assessments Experiencing a Significant Improvement in Symptoms  at Day 30 From baseline	** (**.**)	** (**.**)	0.***
All randomized patients  Experiencing a Significant Improvement in Symptoms  at Day 30 From baseline	** (**.**)	** (**.**)	0.*** 
All patients who had baseline and day 90 assessments Experiencing a Significant Improvement in Symptoms  at Day 90 From baseline	** (**.**)	** (**.**)	0.*** 
All patients on BSC who crossed over to receive RT after day 30 assessments Experiencing a Significant Improvement in Symptoms  at Day 90 from Day 30	NA 	** (**.**)	NA 

 Stratified Cochran-Mantel-Haenszel test adjusting for the stratification factor (HCC versus liver metastases)

 A Significant Improvement in Symptoms is defined as  $\geq 2$  points reduction in worst pain score on BPI.

 Those patients without assessment at day 30 are included in the “no improvement” group.

 Not applicable.

**Table 23: Proportion of Patients Achieving Improvement ( $\geq 2$  points reduction) in Other BPI Scores**

	Baseline to Day 30 			Baseline to Day 90 			Days 30 to 90 
	RT+BSC N (%)	BSC N (%)	CMH P-value 	RT+BSC N (%)	BSC N (%)	CMH P-value 	
Pain at its least	** (**)	** (**)	0.***	** (**)	** (**)	0.***	** (**)
Average pain	** (**)	** (**)	0.***	** (**)	** (**)	0.***	** (**)
Pain Now	** (**)	** (**)	0.***	** (**)	** (**)	0.***	** (**)
Percentage relief in pain by treatment	** (**)	** (**)	0.***	** (**)	** (**)	0.***	** (**)
Pain interference with general activity	** (**)	** (**)	0.***	** (**)	** (**)	0.***	** (**)
Pain interference with mood	** (**)	** (**)	0.***	** (**)	** (**)	0.***	** (**)
Pain interference with walking ability	** (**)	** (**)	0.***	** (**)	** (**)	0.***	** (**)
Pain interference with normal work	** (**)	** (**)	0.***	** (**)	** (**)	0.***	** (**)
Pain interference with relationship	** (**)	** (**)	0.***	** (**)	** (**)	0.***	** (**)
Pain interference with sleep	** (**)	** (**)	0.***	** (**)	** (**)	0.***	** (**)
Pain interference with enjoyment of life	** (**)	** (**)	0.***	** (**)	** (**)	0.***	** (**)

(1) For patients who had baseline and day 30 assessments;

(2) For patients who had baseline and day 90 assessments;

(3) For patients on BSC who crossed over to receive RT Arm after day 30 assessments

(4) Stratified Cochran-Mantel-Haenszel test adjusting for the stratification factor (HCC versus liver metastases)

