To tell us about your abdominal pain/discomfort, you will be provided with a list of numbers and asked to rate your pain/discomfort by choosing **one** number from **0 (no pain/discomfort)** to **10 (pain/discomfort as bad as you can imagine)** that best describes your pain/discomfort in the last 24 hours.

This is what that question looks like:

Please rate your abdominal pain by circling the **one** number that best describes your pain at its **WORST** in the last 24 hours:

0 1 2 3 4 5 6 7 8 9 10
No pain Pain as bad as
you can imagine

Some correct and incorrect sample answers are shown below:

Correct:	0	1	2	3	4	5	6	7	8	9	10	✓
Incorrect:	0	1	2	3	4	5	6	7	8	9	10	✗
Incorrect:	0	1	2	3	4	5	6	7	8	9	10	✗

Now you are ready to fill out Part One of the questionnaire.

If you have any questions or need help, please contact the CRA or study nurse (contact information provided on the cover page).

Thank you for valuable contribution to this research study

Please go to the next page

PART ONE: PATIENT QUESTIONNAIRE – PATIENT TO COMPLETE

CRA / Study Nurse to complete below, in advance:

Please check the timing of the questionnaire:

- Baseline Questionnaire
- 30 day Post-Randomization Questionnaire
- 90 day Post-Randomization Questionnaire

[figure not shown]
NOTE: At the baseline visit, please ask the patient if they would describe their abdominal symptoms as “pain” or “discomfort”. This information will be required at the time of randomization.

Patient describes abdominal symptoms as:

[figure not shown]
- Pain
- Discomfort

Date: _____ - _____ - _____
Day *Month* *Year* Day of week: _____

[figure not shown]
1. Please rate your abdominal pain by circling the **one** number that best describes your pain at its **WORST** in the last 24 hours:

2. Please rate your abdominal pain by circling the **one** number that best describes your pain at its **LEAST** in the past 24 hours.

3. Please rate your abdominal pain by circling the **one** number that best describes your pain on **AVERAGE**.

Please go to the next page

PART ONE: PATIENT QUESTIONNAIRE – PATIENT TO COMPLETE

4. Please rate your abdominal pain by circling the one number that tells how much pain you have **RIGHT NOW.**

[figure not shown]

5. In the last 24 hours, how much relief have pain treatments or medications provided? Please circle the **one** percentage that most shows how much how much **relief** you have received.

[figure not shown]

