### 7.5.3 **Proportion of patients achieving improvement in other BPI pain scores**

For all other BPI scores, the proportions of patients who had a  $\geq 2$  point reduction in from baseline to days 30 and 90 will be calculated among respectively all primary and secondary BPI response evaluable patients and analyzed similarly as the primary endpoint (**Table 23**).

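### SAP Table 23 scores a fall in BPI percentage pain relief as improvement, although on that item more relief is better

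*SAP*

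**What the plan says.** SAP 7.5.3 sets one rule for every BPI item other than worst pain: "For all other BPI scores, the proportions of patients who had a" 2-point-or-larger "point reduction in from baseline to days 30 and 90 will be calculated". The title of Table 23 repeats it ("points reduction) in Other BPI Scores"). The table has eleven rows: pain at its least, average pain, pain now, "Percentage relief in pain by treatment", and seven interference items. Each row carries a CMH p-value at day 30 and at day 90, plus a day 30 to day 90 proportion ("For patients on BSC who crossed over to receive RT Arm after day 30 assessments").

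The relief row corresponds to item 5 of the questionnaire in Protocol Appendix XI: "In the last 24 hours, how much relief have pain treatments or medications provided". The patient answers by circling one percentage ("percentage that most shows how much how much" relief was received).

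SAP Table 21 ("Summary of BPI Scores at Baseline, Day 30 and Day 90") also lists relief among the BPI scores, but gives only N, mean and standard deviation. Protocol 14.2 describes the secondary comparison as a clinically significant change in the favourable direction on the other BPI scores.

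**The concern.** On the pain and interference items a lower score is better, so counting reductions is right. Relief runs the other way. If the shell is programmed as written, the responders in this row are the patients whose relief fell.

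The two-sided CMH tests of that row would be valid tests of the wrong event. If radiotherapy increases relief, the row would show fewer patients improved on RT than on BSC and would contradict the mean relief scores in Table 21.

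The 2-point cut does not carry over either. Protocol 2.5 gives it as a reduction in score, in its account of 0–10 questions. Neither document gives a threshold for a percentage item.

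**Working it through.** There is no stated figure to reproduce, because the point concerns direction of scoring.

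**1. Does the row belong?** SAP 7.5.1 and Protocol 2.5 describe the BPI as 4 intensity and 7 interference items, each scored 0–10. Worst pain is reported in Table 22, which leaves 4 + 7 − 1 = 10 items. Table 23 has 3 intensity + 1 relief + 7 interference = 11 rows. Relief is the extra one.

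**2. Is it exempted anywhere?** The four footnotes to Table 23 define the three patient sets and the test. None mentions direction. SAP 7.5.3 does not name relief, and its wording covers all other BPI scores.

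**3. Does the written rule ever agree with the reversed one?** The response scale is in a figure that is not shown, so steps of 10 from 0 to 100 are assumed. Of 11 × 11 = 121 baseline/follow-up pairs, 55 satisfy baseline − follow-up ≥ 2, a different 55 are increases, and none is in both sets. Recoded 0–10 with a 2-point cut, the counts are 45 and 45, again with no overlap. The lack of overlap does not depend on the step size. On the 0–100 coding, a single one-step fall already passes a 2-point cut.

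**4. Scope.** 11 rows × 2 time points = 22 CMH p-values, of which relief has 2. It also has 1 of the 11 crossover proportions.

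**5. Possible size.** The documents give no mean, SD or coding for relief, so all inputs here are assumptions: change normally distributed and rounded to steps of 10, SD 20 or 30, BSC mean change 0, RT mean rise 5 to 20 points. With a 20-point cut (2 points on 0–10 coding), and with μ the mean change, σ its SD and Φ the normal distribution function:

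- P(fall) = Φ((−15 − μ)/σ)
- P(rise) = 1 − Φ((15 − μ)/σ)

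| Mean change | Fall, SD 20 | Rise, SD 20 | Fall, SD 30 | Rise, SD 30 |
|---|---|---|---|---|
| 0 (BSC) | 0.227 | 0.227 | 0.309 | 0.309 |
| 5 (RT) | 0.159 | 0.309 | 0.252 | 0.369 |
| 10 (RT) | 0.106 | 0.401 | 0.202 | 0.434 |
| 20 (RT) | 0.040 | 0.599 | 0.122 | 0.566 |

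RT minus BSC as written:
- Rise of 5: 0.159 − 0.227 = −0.068 and 0.252 − 0.309 = −0.057.
- Rise of 20: 0.040 − 0.227 = −0.187 and 0.122 − 0.309 = −0.187.

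RT minus BSC scored as an increase:
- Rise of 5: 0.309 − 0.227 = +0.082 and 0.369 − 0.309 = +0.060.
- Rise of 20: 0.599 − 0.227 = +0.372 and 0.566 − 0.309 = +0.257.

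With 21 evaluable patients per arm (the 42 in SAP 2.3, even split assumed), RT responders number 21 × 0.040 to 0.252 = 0.8 to 5.3 as written, against 21 × 0.309 to 0.599 = 6.5 to 12.6 scored as an increase.

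**6. Sensitivity.**
- Coded 0–100, where any one-step change counts (15 becomes 5 in the formulas), RT is 11–37% as written and 50–77% as an increase. BSC is 40–43% either way.
- With a floor at 0 and a ceiling at 100 (simulated; baseline mean 30, 50 or 70, SD 25 assumed; 20-point cut), RT is 3–25% as written and 22–59% as an increase. BSC is 16–30%.

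**The case against.** **The row lies outside the endpoint.** The secondary endpoint and the heading of SAP 7.5.3 refer to BPI pain scores, and relief is not among the items the documents define as the BPI. This is therefore one surplus row in an unfilled shell, and the reference to favourable change in Protocol 14.2 would tell an alert programmer which way to score it. That limits the weight of the point and is a good argument for removing the row. It does not make the row right: the title still says reduction, and reversing it in programming would mean an undocumented choice of direction and cut-off.

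**A fall in relief is not always worsening.** The item asks about relief from treatments or medication. A patient whose pain has eased and who has cut back on analgesics could report little relief from them, and the trial counts opioid reduction as a benefit. This is fair. It makes the effect of radiotherapy on the item hard to predict and weakens the case for scoring an increase as improvement. It gives no support for scoring every sufficient fall as improvement.

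**The effect sizes are illustrative.** This also stands. RT falls below BSC as written because the scenarios assume that RT raises relief and BSC does not. Only the scope count comes from the documents.

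**A new cut-off would be chosen late.** Accrual is closed and the trial is open-label, so setting a responder threshold now costs more than deleting a row.

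**Conclusion.** The concern holds. As written, the relief row of Table 23 counts loss of relief as improvement, contrary to the item's wording and to the favourable change required by Protocol 14.2. Changing the sign alone would not repair it, because the 2-point cut has no stated basis for a percentage.

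The conclusion on direction needs no numerical assumption. The 6 to 19 point apparent deficit for RT depends wholly on the assumed rise, SD and 20-point cut, and shows only how misleading the row could be. The error is confined to this secondary row and should be corrected before the table is produced. The other ten rows, Table 22 and the primary analysis are scored in the right direction.

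**What to change.** Preferred: delete the relief row from Table 23 and state in SAP 7.5.3 that the reduction rule applies to the remaining intensity and interference items. This takes one row and one sentence, with no new data and no change of endpoint. The cost is that relief gets no between-arm test, since Table 21 is descriptive.

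Alternative: keep the row, define improvement as an increase, and state the coding (0–10 or 0–100) and a cut-off suited to a percentage scale before the table is run. Because neither document supplies that cut-off, record it as a late addition and label the row exploratory.

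A separate minor wording point carries no weight here: Protocol 2.5 calls a FACT-TOI change of 7 or more clinically significant, while the endpoint and SAP use 5 or more throughout. Keep the prespecified 5 and reconcile the text. TOI at 7 or more could be added to Table 41 as a labelled sensitivity analysis.

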**Table 24: Opioid and Non-Opioid Intake**

Data set: All Randomized Patients						
	Baseline		Day 30		Day 90	
	RT+BSC	BSC	RT+BSC	BSC	RT+BSC	BSC
Any Opioid Medication Intake						
No	** (**)	** (**)	** (**)	** (**)	** (**)	** (**)
Yes	** (**)	** (**)	** (**)	** (**)	** (**)	** (**)
Generic Opioid Name 						
Opioid #1	** (**)	** (**)	** (**)	** (**)	** (**)	** (**)
Opioid #2	** (**)	** (**)	** (**)	** (**)	** (**)	** (**)
Opioid #3	** (**)	** (**)	** (**)	** (**)	** (**)	** (**)
...	** (**)	** (**)	** (**)	** (**)	** (**)	** (**)
Number of Opioid Taken 						
N	**	**	**	**	**	**
Median	**	**	**	**	**	**
Min - Max	** **	** **	** **	** **	** **	** **
—	—	—	—	—	—	—
Oral morphine equivalents						
N	**	**	**	**	**	**
Median	**	**	**	**	**	**
Min - Max	** **	** **	** **	** **	** **	** **
—	—	—	—	—	—	—
Any Non-Opioid Medication Intake						
No	** (**)	** (**)	** (**)	** (**)	** (**)	** (**)
Yes	** (**)	** (**)	** (**)	** (**)	** (**)	** (**)
Generic Non-Opioid Name 						
Opioid #1	** (**)	** (**)	** (**)	** (**)	** (**)	** (**)
Opioid #2	** (**)	** (**)	** (**)	** (**)	** (**)	** (**)
Opioid #3	** (**)	** (**)	** (**)	** (**)	** (**)	** (**)
...	** (**)	** (**)	** (**)	** (**)	** (**)	** (**)
Number of Non-Opioid Taken 						
N	**	**	**	**	**	**
Median	**	**	**	**	**	**
Min - Max	** **	** **	** **	** **	** **	** **
—	—	—	—	—	—	—

 Patient may have more than one opioid or non-opioid medications.

**Table 25: Proportion of Patients with Reduction in Opioid Use at Day 30**

Patients who have completed Pain/Discomfort and Medication Questionnaires at baseline and day 30	RT+BSC N (%)	BSC N (%)	CMH P-value 
Patients with 25% Reduction in Opioid Use 	** (**.**)	** (**.**)	0.***

 Stratified Cochran-Mantel-Haenszel test adjusting for the stratification factor (HCC versus liver metastases) 25% Reduction in opioid use from baseline to day 30 (employing daily morphine equivalence scale).**Table 26: Proportion of Patients with Improved BPI and no Increasing Opioid Use at Day 30**

Patients who have completed Pain/Discomfort and Medication Questionnaires at baseline and day 30	RT+BSC N (%)	BSC N (%)	CMH P-value (*)
Patients with Improved BPI and no Increasing Opioid Use	** (**.**)	** (**.**)	0.***

\* Stratified Cochran-Mantel-Haenszel test adjusting for the stratification factor (HCC versus liver metastases)

**Table 27: All Deaths**

Number of Patients who died	Data set: All Randomized Patients		Number of Patients (%)
	RT+BSC N=**	BSC N=**	
	** (**)	** (**)	
Cause of Death			
Cancer Only	**	**	
Adverse Event Possibly/Probably/Definitely Related Protocol Treatment	**	**	
Complication from a Non-protocol treatment for This Malignancy	**	**	
Other Primary Malignancy	**	**	
Other Condition or Circumstance	**	**	

**Table 28: Kaplan-Meier Estimate for Proportion of Patients Alive at Day 90**

Data set: All Randomized Patients			
	N	Kaplan-Meier Estimate for Proportion of Patients Alive at Day 90 (95% CI)	Log Rank P-value (*)
Treatment Arm			0.***
RT+BSC	**	**.** (**.**, **.**)	
BSC	**	**.** (**.**, **.**)	

\* Stratified Log Rank test adjusting for the stratification factor (HCC versus liver metastases)

**Table 29: Grade 2 or Higher Adverse Events**

	Number of patients (%)			
	Day 30 After Randomization for All Treated Patients on RT+BSC (N=**)			
	2	3	4	5
Patients with any AE	** (**)	** (**)	** (**)	** (**)
Patients with AE within category				
Category 1 				
Event 1	** (**)	** (**)	** (**)	** (**)
Event 2	** (**)	** (**)	** (**)	** (**)
Event 3	** (**)	** (**)	** (**)	** (**)
...	** (**)	** (**)	** (**)	** (**)
	** (**)	** (**)	** (**)	** (**)
Category 2 				
Event 1	** (**)	** (**)	** (**)	** (**)
...	** (**)	** (**)	** (**)	** (**)
	** (**)	** (**)	** (**)	** (**)
Day 90 After Randomization for All Treated Patients on RT+BSC (N=**)				
	2	3	4	5
Patients with any AE	** (**)	** (**)	** (**)	** (**)
Patients with AE within category				
Category 1 				
Event 1	** (**)	** (**)	** (**)	** (**)
Event 2	** (**)	** (**)	** (**)	** (**)
Event 3	** (**)	** (**)	** (**)	** (**)
...	** (**)	** (**)	** (**)	** (**)
Category 2 				
Event 1	** (**)	** (**)	** (**)	** (**)
...	** (**)	** (**)	** (**)	** (**)
	** (**)	** (**)	** (**)	** (**)

(1) Patients may have more than one event within a category.

**Note: The same type of table will be made for BSC arm and at day 90 only for patients on BSC who crossed over to RT after day 30 assessment.**

